6.2.3.3 Lost to Follow-up

Subjects who miss postoperative study visits and cannot be contacted within a reasonable timeframe via letter or telephone, will be considered lost to follow-up. The site will make at least three attempts to contact the subject via telephone. If unsuccessful, the site will send a letter to the subject. The letter will request the subject to contact and return to the study site. If the subject does not contact the site within a week after the letter was received, he/she will be considered lost to follow-up, and the site will send a second letter to notify the subject of study exit due to lack of response to the telephone calls and first registered letter. A Study Exit CRF may then be completed for the subject.

All attempts to contact the subject (including telephone call logs, copies of letters) must be documented and maintained with the subject's study source documentation.

6.2.4 STUDY TERMINATION

The study may be terminated by Glaukos at any time following appropriate notification to the study site and subjects.

6.3 Procedures

Study visits and assessments are listed below; a table overview of study procedures by visit is provided in [APPENDIX A: SCHEDULE OF VISITS AND MEASUREMENTS](#)

6.3.1 DURATION OF STUDY

Following the initial implantation, the treatment period will be 3 months in duration.

[figure not shown]
[figure not shown]
6.3.2 ENROLLMENT

[figure not shown]
All subjects must give written informed consent before undergoing any study-related change in their treatment or any study related procedures.

6.3.3 PREOPERATIVE PROCEDURES

6.3.3.1 Visit 1 (Screening)

[figure not shown]

[figure not shown]

If the subject is ineligible for the study, complete the appropriate CRF.

[figure not shown]
6.3.4 TREATMENT PROCEDURES

6.3.4.1 Visit 2 (Operative Exchange Day 0)

[figure not shown]

6.3.4.2 Visit 3 (Day 1 Post-Exchange, 1 days)

[figure not shown]

6.3.4.3 Visit 4 (Day 10 Post-Exchange, 10 ± 3 days)

[figure not shown]

6.3.4.4 Visit 5 (Week 4 Post-Exchange, 28 days ± 3)

[figure not shown]

[figure not shown]
6.3.4.5 Visit 6 (Month 3 Post-Exchange, 91 days \pm 14)

6.3.4.6 Visit 7 (Month 6 Post-Exchange, 182 days \pm 30)

6.3.4.7 Visit 8 (Month 12 Post-Exchange, 365 days ± 30)

6.4 Concomitant Therapies

6.4.1 MEDICATIONS OR TREATMENTS

Therapy considered necessary for the subject's welfare that will not interfere with the evaluation of the study medication may be given at the discretion of the investigator.

6.4.2 USE OF CONTACT LENSES

Contact lens wear is allowed in this study. Subjects are to be instructed to remove their contact lenses in the study eye prior to instillation of study medications and to wait for 20 minutes before inserting their contact lenses after instillation of medication.

6.5 Post-Treatment Management of IOP and Rescue Medications

7 EXTENT OF EXPOSURE AND TREATMENT COMPLIANCE

All subjects will be implanted with a second Travoprost Intraocular Implant to exchange with the previously implanted first one that will be explanted. All subjects will be followed for the duration of the study.

8 STATISTICAL ANALYSES

One database lock is planned after all subjects have exited from the study. Prior to the database lock, a Statistical Analysis Plan (SAP) will be approved.

8.1 Sample Size

8.2 Analysis Populations

All subjects who undergo the exchange procedure will be included in the safety population. The safety population will be used for all data tabulations and listings.

8.3 General Statistical Methods

All demographic and safety data collected will be displayed in data listings. No formal statistical testing will be performed.

Continuous measures will be summarized with descriptive statistics including the number of observations, mean, standard deviation, median, minimum, and maximum. Summary statistics for categorical measures include the percentage and number of cases.

8.4 Efficacy Analyses

There are no efficacy measures in this study. IOP is evaluated for safety.

8.5 Safety Analyses

8.5.1 ADVERSE EVENTS

Adverse events (AEs) in the study eye will be coded using the Medical Dictionary for Regulatory Activities (MedDRA) nomenclature. Treatment Emergent Adverse Events (TEAE) are defined as those AEs that occur after the initial treatment at Visit 2 (Operative Exchange Day 0).

AEs that occur on the date of the procedure are classified as either intra-operative or post-operative. Post-operative AEs are considered to be TEAEs. Intra-operative AEs and TEAEs will be summarized separately and presented in separate listings.

A line listing of serious adverse events will be provided.

8.5.2 OTHER SAFETY MEASURES

Details of analyses for other safety measures (see [Section 5.2](#)) will be provided in the SAP.

8.6 Interim Analyses

No interim analyses are planned.

9 ADVERSE EVENTS

An Adverse Event (AE) is defined as any untoward and unintended medical occurrence (e.g., sign, symptom, disease, syndrome, intercurrent illness) that occurs in a study subject, regardless of the suspected cause during the study. Adverse events will be clearly documented on the study source document and monitored throughout the course of the study.

Events occurring after signing the informed consent but prior to the implant or procedure should be documented in the medical history. Events observed during or after the initial implant or exchange procedure until the final study visit, are to be recorded as AEs if they are in the study eye and deemed related to the implant or procedure.

Any clinically significant change in a subject's condition after receiving the study treatments, regardless of causality, is to be considered an adverse event, unless the change is determined to be a continuation of a pre-existing condition that is documented in the subject's medical history. If an adverse event occurs, an AE form must be completed.

An AE includes any of the following:

- An exacerbation or an unexpected increase in frequency or intensity of a pre-existing condition, including intermittent or episodic conditions
- New conditions or illnesses detected or diagnosed after the implant procedure
- A suspected interaction with any of the study treatments
- Signs, symptoms, or the clinical sequelae of a suspected overdose of either any of the study treatments or a concomitant medication
- Any clinically significant laboratory finding that was not present prior to receiving any of the study treatments

An AE does NOT include any of the following:

- Anticipated day-to-day fluctuations of any pre-existing conditions, including the disease under study (OAG and OHT).
- Medical or surgical procedure, (e.g., colonoscopy or hernia repair). The condition that led to the procedure may be an AE, if not present in medical history.
- Hospitalizations where an untoward medical occurrence did not occur (social or convenience admission to the hospital).
- Pre-existing conditions or diseases that were present before receiving any of the study treatments that do not worsen or that are chronic but stable
- Changes in a chronic condition or disease that are consistent with natural disease progression. (These medical conditions should be adequately documented).
- Lack of efficacy of the study treatment for the condition being investigated.

AEs will be graded on a 3-point scale and reported in detail as indicated on the CRF:

Mild: easily tolerated, causing minimal discomfort and not interfering with normal everyday activities

Moderate: sufficiently discomforting to interfere with normal everyday activities

Severe: incapacitating and/or preventing normal everyday activities

The relationship of each AE to study treatment should be determined by the investigator using the following explanations:

Definitely Unrelated: the event is clearly related to other factors such as the subject's clinical state, therapeutic interventions, or concomitant medications administered to the subject

Unlikely Related: the event is most likely produced by other factors such as the subject's clinical state, therapeutic interventions, or concomitant medications administered to the subject; and does not follow a known response pattern to the study medication

Possibly Related: the event follows a reasonable temporal sequence from the time of drug administration; and/or follows a known response pattern to the study medication; but could have been produced by other factors such as the subject's clinical state, therapeutic interventions, or concomitant medications administered to the subject

Probably Related: the event follows a reasonable temporal sequence from the time of drug administration; and/or follows a known response pattern to the study medication; and is not likely to have been produced by other factors such as the subject's clinical state, therapeutic interventions, or concomitant medications administered to the subject

Definitely Related: the event follows a reasonable temporal sequence from the time of drug administration; and follows a known response pattern to the study medication; and cannot be reasonably explained by other factors such as the subject's clinical state, therapeutic interventions, or concomitant medications administered to the subject

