3 STUDY DESIGN

This is a prospective, non-randomized, open-label, multi-center, single arm, clinical trial of the safety of the exchange of the Travoprost Intraocular Implant in subjects who were previously implanted with the Travoprost Intraocular Implant in the GC-009 study (1st Cycle). Approximately [REDACTED] [REDACTED] will be enrolled into this study and will be followed through 12 months postoperative.

Screening Procedure:

After providing informed consent, prospective subjects will be evaluated against the Screening criteria. At Visit 1 (Screening), all subjects must meet all entry criteria.

Subjects who qualify at Visit 1 (Screening) may be scheduled for Visit 2 (Operative Exchange Day 0) on a separate day.

The eye previously implanted with a Travoprost Intraocular Implant in the GC-009 study (study eye) will be assessed at Visit 1 (Screening). The subject may then be scheduled for study treatment. Subjects will be treated unilaterally, only the implanted eye (study eye) will go through the study treatment. The fellow eye will be treated outside the parameters of the study per investigator discretion using their standard of care options.

Treatment Procedure:

The Operative and Postoperative scheduled visits are listed in the following table:

Visit Number	Visit Timepoint
2	Operative Exchange Day 0
3	Day 1 Post-Exchange
4	Day 10 Post-Exchange (10 days \pm 3)
5	Week 4 Post-Exchange (28 days \pm 3)
6	Month 3 Post-Exchange (91 days \pm 14)
7	Month 6 Post-Exchange (182 days \pm 30)
8	Month 12 Post-Exchange (365 days \pm 30)

At Visit 2 (Operative Exchange Day 0), subjects will have the first implant which was inserted in Study GC-009 exchanged with a second G2TR-█ implant.

At Visit 1 (Screening), IOP can be measured at any time. At all other scheduled visits, Day 10 Post-Exchange, Week 4 Post-Exchange, Month 3 Post-Exchange, Month 6 Post-Exchange, and Month 12 Post-Exchange), IOP measurements will be taken once daily at the same time as screening \pm 60 minutes. Study follow-up will continue until Visit 8 (Month 12 Post-Exchange), after which subjects will be exited from the study.

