6.2 Eligibility Requirements

6.2.1 INCLUSION CRITERIA

6.2.1.1 Visit 1 (Screening) Inclusion Criteria

At the Visit 1 (Screening), all subjects must meet the following criteria:

- 1) Subject status as follows:
 - a. able and willing to attend scheduled follow-up exams for the duration of the study
 - b. able and willing to provide written informed consent on the IRB/IEC-approved Informed Consent Form
- 2) Best spectacle corrected visual acuity of 20/80 or better in each eye.
- 3) Previously implanted with the Travoprost Intraocular Implant in the GC-009 study that is present in the study eye (1st Cycle). Only the eye with the Travoprost Intraocular Implant may be assessed for exchange at Visit 1 (Screening).

All subjects (OAG and OHT) must meet the rest of the following criteria:

- 4) Angle anatomy defined as follows:

a.

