6.2.2 EXCLUSION CRITERIA

6.2.2.1 Visit 1 (Screening) Exclusion Criteria

Subjects who meet any of the following criteria in the study eye at Visit 1 (Screening) are not eligible to participate in the study:

1) Glaucoma status as follows:

- a. traumatic, uveitic, neovascular, or angle-closure glaucoma; or glaucoma associated with vascular disorders

b. [REDACTED]

[REDACTED]

[REDACTED]

2) Corneal status as follows:

- a. any active inflammation or edema [REDACTED]

- b. clinically significant dystrophy [REDACTED]

[REDACTED]

e. [REDACTED]

[REDACTED] during the course of the study, that may interfere with IOP measurement reliability

- f. opacities or disorders that would inhibit visualization of the nasal angle.

3) Congenital or traumatic cataract [REDACTED]

4) [REDACTED]

[REDACTED]

[REDACTED]

[REDACTED]

[REDACTED]

6) Other ocular status as follows:

- a. clinically significant sequelae from trauma [REDACTED]
- b. history or chronic ocular inflammatory disease or presence of active ocular inflammation [REDACTED]

7) Fellow eye status as follows:

- a. fellow eye actively enrolled in this trial or any other clinical trial.

8) Subject status as follows:

- a. pregnant or planning to become pregnant during the course of the study
- b. uncontrolled systemic disease (e.g., diabetes, hypertension) that could compromise their participation in the study
- c. current participation in any study, or participation within 30 calendar days of Visit 1 (Screening)
- d. immunodeficiency conditions

e. [REDACTED]

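### Protocol Section 9 sends implant-related study-eye events between consent and the exchange to medical history, so prompt safety reporting is not clearly triggered while the first implant is still in the eye

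*Protocol*

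**What the plan says.** Two adjacent sentences in Protocol Section 9 set the recording window. The first reads "Events occurring after signing the informed consent but prior to the implant or procedure should be documented in the medical history". The second reads "Events observed during or after the initial implant or exchange procedure until the final study visit, are to be recorded as AEs", with a condition: such events "are to be recorded as AEs if they are in the study eye and deemed related to the implant or procedure".

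The same section opens with a wider definition: an AE is any untoward occurrence "that occurs in a study subject, regardless of the suspected cause during the study".

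The first implant predates this study. At Visit 2, "subjects will have the first implant which was inserted in Study GC-009 exchanged with a second" implant (Protocol Section 3). Inclusion criterion 3 requires that implant to be in place at screening: "Previously implanted with the Travoprost Intraocular Implant in the GC-009 study that is present in the study eye (1st Cycle").

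Screening and surgery are separated in time: "Subjects who qualify at Visit 1 (Screening) may be scheduled for Visit 2 (Operative Exchange Day 0) on a separate day". The visible text gives no maximum gap.

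**The concern.** A rule that treats everything before the procedure as history suits a first-implant trial, where no investigational product is in the eye beforehand. Here the product is present from consent onward, and removing it is part of the procedure under study. An event caused by the first implant after consent is therefore a possible reaction to investigational product in a consented subject, yet Section 9 files it as background.

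The main stake is prompt reporting. Sections 9.1 and 9.2 ask for serious and unexpected adverse events to reach the sponsor immediately, preferably within 24 hours. An event that is never classed as an AE does not clearly fall under either section. A second stake is attribution. The objective is the safety of the exchange in eyes that already hold an implant, so effects of the first implant should be identifiable as such.

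**Working it through.** No arithmetic applies: no rate, power or sample-size figure is involved. The check is a comparison of texts.

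**Step 1. What does *initial implant* mean?** The visible text does not define it.

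- For Visit 2: Protocol 8.5.1 places the initial treatment at Visit 2. Protocol 6.3.1 uses *initial implantation* for the start of this study's treatment period. SAP 7.1.2 starts TEAEs when the exchange surgery begins, and SAP 4.1.1 ties baseline to the second implant. The medical-history sentence speaks of a time after consent but before the implant; if that were the GC-009 implant, which predates consent, no such time would exist.
- For GC-009: the sentence names the initial implant and the exchange procedure as alternatives, which is nearly redundant if both mean Visit 2. Protocol Sections 3, 6.1 and 7 call the GC-009 implant the first and the Visit 2 implant the second.

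Visit 2 is the better-supported reading, but a site could reasonably take the other.

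**Step 2. Classify an event with onset between consent and the exchange under the two window sentences.**

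| Reading of *initial implant* | Event | Classification | Where it appears |
|---|---|---|---|
| Visit 2 | Any, including study eye and related to the first implant | Medical history only | SAP 5.4 table and listing, if exchanged |
| GC-009 | Study eye, related | Both history and AE | SAP 5.4, and the listing of all AEs (SAP 7.1.2), if exchanged; no TEAE table |
| GC-009 | Unrelated, or not in the study eye | Medical history only | SAP 5.4, if exchanged |
| Either | Subject never exchanged | As above | Only the screen-failure reason is certain (SAP 5.1) |

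The last row follows from Protocol 8.2 and SAP Section 3: the safety set contains only exchanged subjects and is used for all tabulations and listings.

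**Step 3. Compare with the other reporting text.** The general AE definition covers the whole study. Appendix B requires investigators to report adverse experiences arising in the course of the investigation to the sponsor and the IRB, with no start-of-treatment limit. Both reach into the interval that the Visit 2 reading excludes. A later item in Appendix B refers to events while a subject is enrolled, and SAP 5.1 counts a subject as enrolled only at surgery. A site is thus given rules that differ for the same event.

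**Step 4. Could GC-009 capture it?** Criterion 8c excludes "current participation in any study, or participation within 30 calendar days of Visit 1 (Screening"), with no visible exception for GC-009. That suggests GC-009 collection should have ended, but its follow-up rules are not in the documents.

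**The case against.** The case against making much of this is substantial, and most of it stands.

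- A reader might infer that such an event is both history and an AE and also goes unreported. No single reading gives both. Double classification needs the GC-009 reading; the loss of AE status needs the Visit 2 reading.
- Even on the GC-009 reading the overlap does not cover every event, only study-eye events deemed related.
- A reader might infer that the event is never reported. For exchanged subjects, history is tabulated by SOC and PT and listed (SAP 5.4). The accurate statement is that it is not reported as an AE.
- A reader might infer that the event reaches the sponsor under neither protocol. Appendix B keeps a general duty, Section 9.1 opens by describing serious events broadly as findings that suggest a significant hazard, and GC-009's rules are unseen. The documents do not establish a complete gap.
- An event filed as history is not lost for good if it gets worse: Section 9 counts an exacerbation after the exchange as an AE. Only a stable continuation is exempt.
- Visit procedures and the schedule are not shown, and may contain a relevant instruction or a limit on the screening interval.

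What the objection does not remove is the stated rule itself. Section 9 gives a specific instruction to use medical history while an investigational implant is in the eye, and that instruction disagrees with the section's own definition and with Appendix B. Defining *initial implant* as Visit 2 would end the ambiguity but would make the exclusion firm.

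**Conclusion.** A limited defect holds. On the better-supported reading, a study-eye event related to the first implant, with onset between consent and the exchange, is not recorded as an AE, and the reporting in Sections 9.1 and 9.2 is not clearly triggered. On the less likely reading the two sentences overlap for such events.

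Every exchanged subject (approximately 45, Protocol 6.1) passes through the interval, as does anyone who consents and is not exchanged. The documents give no event rate and no visible maximum interval, so the number of affected events cannot be estimated. Subjects never exchanged are the weakest spot, since an implant-related event may itself be why surgery did not go ahead.

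TEAE tables are unaffected, because Protocol 8.5.1 and SAP 7.1.2 both start TEAEs at Visit 2. The conclusion assumes that the unseen visit procedures do not already provide for pre-exchange events; if they do, Section 9 should still be made to agree with them. This is a cheap improvement to safety reporting. Section 9's separate tension between recording events of any cause and only related ones lies outside this point.

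**What to change.** 1. In Protocol Section 9, replace *initial implant* with *exchange procedure at Visit 2*.
2. Add that study-eye events deemed related to the first-cycle implant, with onset from consent to the start of the exchange, are recorded as AEs, flagged *pre-exchange*, and subject to Sections 9.1 and 9.2. Other events in that interval stay in medical history, so the existing eye and relatedness limits are unchanged.
3. In SAP 7.1.2, keep flagged events out of all TEAE tables and list them separately for all consented subjects.
4. In Protocol 8.2 and SAP Section 3, state an exception to the safety-set rule for that listing. Without it, subjects never exchanged would be left out.

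The cost is short protocol and SAP edits, a CRF flag with a field for attribution to the first implant (the relatedness scale in Section 9 refers to study treatment), one listing, and a few more AE forms. No planned summary table changes.

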The study objective is to evaluate the safety of the surgical exchange procedure of Travoprost Intraocular Implant in subjects with a previously implanted Travoprost Intraocular Implant.

STUDY TREATMENTS

Subjects will undergo an exchange of a Travoprost Intraocular Implant through a small temporal clear corneal incision.

Structure: Single arm

Number of Centers: Approximately 15 centers

Masking: Open-label

Method of Subject Assignment:

After Visit 1 (Screening), qualified subjects will be scheduled to undergo treatment with the G2TR-█ implant.

Randomization: No

Total Sample Size: Approximately [REDACTED] subjects

Statistical Rationale Provided: Please refer to Statistical Section, [Section 8](#)

STUDY OVERVIEW

Subjects will be assessed for inclusion/exclusion criteria at Visit 1 (Screening). At this visit, all subjects must meet all entry criteria. Subjects who meet criteria at Visit 1 (Screening) may be scheduled for Visit 2 (Operative Exchange Day 0) (on a separate day).

Visit Schedule:

This study will consist of 8 visits over approximately a 12 month period: Visit 1 (Screening), Visit 2 (Operative Exchange Day 0), Visit 3 (Day 1 Post-Exchange), Visit 4 (Day 10 Post-Exchange), Visit 5 (Week 4 Post-Exchange), Visit 6 (Month 3 Post-Exchange), Visit 7 (Month 6 Post-Exchange), and Visit 8 (Month 12 Post-Exchange).

Study Measures will be collected for the study eye only:

Safety

- Intra-operative adverse events
- Post-operative adverse events
- Corrected visual acuity (logMAR score using ETDRS chart)
- Slit-lamp biomicroscopy findings
- Gonioscopy findings
- Specular microscopy findings
- Intraocular Pressure
- Ophthalmoscopy findings
- Visual field evaluation

Other

- Operative and surgical assessments

Specified Plan for Data Analysis: Yes (refer to [Section 8](#))

Power and Sample Size: The sample size of [REDACTED] who undergo an exchange of a Travoprost Intraocular Implant was determined empirically. This sample size is considered adequate to support the objective of this study.

STUDY VARIABLES AND STATISTICAL ANALYSIS

Efficacy Variable

There is no efficacy variable in this study. Intraocular pressure is assessed for safety.

Safety Variables

Adverse events (intra-operative and post-operative [TEAEs]) in the study eye will be monitored and summarized.

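### Protocol Section 9 gives conflicting rules on which adverse events are recorded, and its study-eye limit does not fit the SAP's non-ocular and non-study-eye tables

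*Protocol*

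**What the plan says.** Protocol Section 9 opens with a definition of an adverse event that has no limit on cause or body site. It adds that "Adverse events will be clearly documented on the study source document and monitored throughout the course of the study". The next paragraph narrows this: events seen during or after the procedure, up to the final visit, "are to be recorded as AEs if they are in the study eye and deemed related to the implant or procedure". The paragraph after that widens it again. A clinically significant change after treatment, "regardless of causality, is to be considered an adverse event" (unless it continues a documented pre-existing condition), and "If an adverse event occurs, an AE form must be completed".

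On causality, Section 9 states that "The relationship of each AE to study treatment should be determined by the investigator", on a five-point scale that runs from definitely unrelated to definitely related. SAP 7.1.2 confirms that the CRF uses these five categories. It counts the top three, and missing values, as related.

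On location, the Synopsis states that "Study Measures will be collected for the study eye only", above a list that begins with intra-operative and post-operative adverse events. It also states that "Adverse events (intra-operative and post-operative [TEAEs]) in the study eye will be monitored and summarized". Protocol 8.5.1 speaks of coding events in the study eye, but adds without any eye limit that "A line listing of serious adverse events will be provided". SAP 7.1.2 goes further. It plans four ocular and four non-ocular TEAE tables by SOC and PT, with study-eye, non-study-eye and overall groups in every ocular table. SAP Section 10 declares no change from the protocol-planned analyses.

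**The concern.** The only objective is the safety of the exchange procedure. The trial has a single arm, is open-label and does no formal testing, so the descriptive adverse event tables are a main result, and no control arm would reveal under-recording.

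If sites follow the recording sentence, an investigator's opinion on causality decides whether an event enters the dataset at all, when it should be an attribute of an event already recorded. Two kinds of event can then be lost: study-eye events judged unrelated, and every event outside the study eye, even a related one. Omission works in one direction, so all-cause study-eye incidence can only be understated. In the non-ocular and non-study-eye tables, a zero could mean that nothing occurred or that nothing was collected. If different sites follow different sentences, the pooled figures mix two definitions.

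**Working it through.** The plan gives no figure to reproduce on this point. The check sets the rules side by side and then works out what each would leave in the SAP tables.

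**1. Rules on cause**

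| Place | Rule |
|---|---|
| Protocol 9, definition | any suspected cause |
| Protocol 9, recording sentence | deemed related |
| Protocol 9, next paragraph | any cause; a form for every event |
| Protocol 9, causality scale | every event rated; two of the five categories are on the unrelated side |
| SAP 7.1.2 | related TEAEs tabulated as a subset of all TEAEs |

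Treating the first row as a definition and the second as a narrower recording rule does not remove the conflict, because the third row attaches a form to every event. Under the second row, the two unrelated categories would go essentially unused, and the related ocular tables would largely repeat the all-event ocular tables.

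**2. Rules on location**

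| Place | Rule |
|---|---|
| Synopsis | study eye only |
| Protocol 8.5.1 | study eye for coding (no explicit exclusion of others); SAE listing without an eye limit |
| Protocol 9, definition | anywhere in the subject |
| Protocol 9, recording sentence | study eye |
| SAP 7.1.2 | study eye, non-study eye and non-ocular |

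Two places give weaker support for the broad scope. Protocol 9.1 counts a threat to the sight of either eye as serious, and Appendix B asks investigators to report all adverse medical events.

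**3. Effect of the location limit on the tables in SAP 7.1.2**

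- SOC/PT tables: 4 ocular + 4 non-ocular = 8. Non-ocular share: 4 of 8.
- Ocular column groups: 4 tables × 3 groups = 12. Non-study-eye share: 4 of 12.
- Under the recording sentence alone, all of these are empty, and each overall column equals its study-eye column.
- If SAE reports (Protocol 9.1) or unexpected-event reports (Protocol 9.2) are also entered in the dataset, these cells are incomplete rather than empty.

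**4. Effect of the relatedness limit on study-eye incidence**

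Inputs: n = about 45 (Protocol 6.1); k = number of subjects who had study-eye events, all of which were left out as unrelated. The documents do not give k, so the values below are assumed.

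Fall in all-cause study-eye incidence = k / n

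- k = 1: 1/45 = 2.2 percentage points
- k = 3: 3/45 = 6.7 percentage points
- k = 5: 5/45 = 11.1 percentage points

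**The case against.** The strongest reply is that the recording sentence is the outlier on cause. The definition, the form requirement, the causality scale and the source-record requirement (Protocol 15.1) are not limited to related events, and SAP 7.1.2 reports that the CRF carries the unrelated categories. Sites may well have recorded everything, in which case no data were lost. The sentence also says if, without an only. Text not visible to us (CRF instructions, visit-by-visit procedures, visit schedules) might settle the matter. This stands as far as it goes: the loss of data is conditional, and the rule applied in practice cannot be read from the public text. It does not remove the contradiction. The two conditions in the sentence do nothing unless they restrict recording, and a site that follows them complies with a written instruction.

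On location, the Synopsis, Protocol 8.5.1 and the recording sentence all point to the study eye, so this part is mainly a scope mismatch between protocol and SAP. That is fair. Protocol 9.1 concerns seriousness, and Appendix B is a general reporting duty, so neither decides the point. SAP 7.1.2 alone is enough to establish the mismatch.

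It can also be said that related study-eye events, the core of the objective, survive even the narrow rule. SAEs and unexpected events have their own reporting routes, and the examination-based summaries in SAP 7.1.3 are untouched. All of this limits the damage. But no text says that events reported by those routes enter the adverse event tables, and judging relatedness before recording is a poor filter in a trial that exists to describe safety. Finally, the values of k are illustrations and are not evidence of loss.

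**Conclusion.** The concern holds on both parts. Protocol Section 9 gives incompatible rules on whether an unrelated event is recorded, and the study-eye scope in the protocol does not match the scope tabulated in SAP 7.1.2, although SAP Section 10 declares no change.

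The textual conflict is certain and does not come from redaction. Its effect on the table layout is exact if the recording sentence is applied alone: 4 of 8 SOC/PT tables and 4 of 12 ocular column groups have no possible entries. Its effect on study-eye incidence is conditional: 2.2 percentage points per affected subject, with about 45 treated and the number affected unknown. Because safety is the sole objective, the rules must be reconciled before the adverse event tables can be interpreted.

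**What to change.** 1. **Protocol 9.** Replace the competing sentences with one capture rule that does not depend on relatedness. As a minimum, record all study-eye events from the start of the exchange surgery to the final visit, plus all SAEs and deaths, with relationship held as a separate field.
2. **Location scope.** State it once and apply it in the Synopsis, Protocol 8.5.1, Protocol 9 and SAP 7.1.2. Either record all events, or keep the study-eye scope and remove the non-ocular and non-study-eye tabulations. If those tabulations are kept, label them as not systematically collected apart from SAEs and deaths.
3. **SAP Section 10.** Declare any remaining difference from the protocol's study-eye scope.

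The cost is a set of wording changes, a clarification to about 15 sites, and extra adverse event entries for about 45 subjects. The number of entries depends on the scope chosen. No visit or procedure is added.

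If collection is complete, state the rule that sites actually applied in a SAP amendment before lock or in the study report, as SAP Section 1 allows. That makes the tables interpretable but does not recover events that were never entered.
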